## **Objectives**

The objective of this study is to evaluate the positional stability and quality of lung isolation provided by the EZ-blocker compared to a DLT for both right and left sided thoracic surgery.

An additional objective will be to assess time to placement of both devices and other significant clinical differences between these two approaches to placement of the BB including airway injury and post-operatives sore throat, post-operative hoarseness, Additionally we would like to examine the preoperative high resolution CT imaging data to determine if there are anatomic landmarks that may potentially inform the appropriateness or inappropriateness of choosing an EZ-blocker or left sided DLT.

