The surgeon will be blinded to technique and queried as to the quality of isolation upon entry into the chest and this will be recorded. This will be queried every 60 minutes for the duration of the procedure.

We will record any episodes of loss of isolation and details of repositioning including times and the issue of malposition i.e. the blocker or DLT slipped out or slipped in too far. We will record any episodes of ongoing desaturation which require deflation of the EZ-blocker cuff and/or ventilation of both lungs with a DLT.

We will record the point at which the surgeon the end of OLV. The patient will be extubated according to normal clinical practices and will be taken to the post anesthesia care unit. The Ez-blocker will be removed simultaneously with the ETT. In patients in the EZ-blocker group that remains intubated post procedure the EZ-blocker will be removed prior to going to the ICU. In the DLT group the DLT will be exchanged according to routine clinical practice to a single lumen ETT.

The patient will be contacted on post-operative days 1 and 2 to assessed for hoarseness and sore throat via a VAS scale from 0-100: 0=No sore throat and 100=the worst sore throat imaginable. We will also record any significant morbidity or mortality events such as prolonged mechanical ventilation or cardiac arrest or stroke that may occur within the first 2 post-operative days.

In patients where isolation is troublesome requiring multiple repositioning we will evaluate their preoperative CT scan to determine if there are any anatomical findings on CT which maybe predictive of failure. We will compare these to an equivalent number of control patients from this study population in which isolation was successful. We will attempt to match these patients for size and diagnosis.

The study will be performed at Wake Forest Baptist Medical Center a tertiary academic medical center.

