### **Interventions and Interactions**

Interventions and interactions for the patient should be fairly reasonable. The largest overall commitment of time from the patient will be in the PAC at the time of recruitment or in their room as an inpatient. One of the PAC attendings, or investigators, or study personnel will interview the patient explain the study and attempt to recruit the patient if they are eligible. The study participant will have their questions answered and will be consented.

On the day of surgery, the patient will be identified in the holding area and a study representative will make sure that he or she has not changed their mind about participation and will answer any questions the study subject may have thought of since the interview in PAC. If the patient is still in agreement to participate in the study they will be taken to the OR and care will proceed as it would otherwise with the induction of general anesthesia and placement of the EZ-blocker or DLT per the protocol depending on which group the patient has been randomized to. In some cases, in which the patient is an inpatient or does not go to the PAC a member of the study team may approach them to participate either the day before or on the day of surgery. After the surgery, a study representative will contact the patient to evaluate for any postoperative issues such as a sore throat or increase hoarseness on post-operative days 1 and 2. This will be the last interaction of the patient with the study.

	Patient identified in PAC.	Patient approached in PAC and questions answered about. Patient to sign consent for study participation here.	Confirmation and randomization on day of surgery	Bronchial Blocker placed intraluminally or extraluminally. Data collected about placement	Patient will undergo surgery. Intra-operative events related to blocker position will be recorded	At the end of surgery BB or DLT will be removed, and the patient will extubated, and patient taken to PACU or ICU	Patient interviewed on post-op days 1 and 2 to evaluate sore throat.
Time required of Patient	0 min	20 min	5 min	10 min	Depends on surgical duration.		5-10 min

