### **Outcome Measure(s)**

We will measure the number of DLT or BB replacements, time of placement, quality of isolation at 1-hour intervals during the operation, incidence of sore throat and/or hoarseness postoperatively.

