## Appendix 1 Data Sheet

### Data Form for EZ-bronchial Blocker vs. Double Lumen Study

Patient Sticker

ASA:

Weight:      Height:      BMI:

Gender:

Diagnosis:

Laterality:      RIGHT      LEFT

EZ-Blocker      DOUBLE LUMEN

Induction Drug Doses:

Propofol \_\_\_\_\_      Fentanyl \_\_\_\_\_      Rocuronium(0.8mg/kg) \_\_\_\_\_  
Etomidate \_\_\_\_\_

Ventilate/Wait 3 minutes at least.

Begin Blocker or Double Lumen with DL. START TIMING:

Time for placement of EZ-blocker or DLT: \_\_\_\_\_

Number of EZ-blocker or DLT Replacements During Procedure: \_\_\_\_\_

Quality of Isolation: 1- Excellent      2 – Fair      3 - Poor

Time 1 \_\_\_\_\_      Quality of Isolation T1 \_\_\_\_\_

Time 60 min      Quality of Isolation 60 \_\_\_\_\_

Time 120 min      Quality of Isolation 120 \_\_\_\_\_

Time 180 min      Quality of Isolation 180 \_\_\_\_\_

Time 240 min      Quality of Isolation 240 \_\_\_\_\_

Time 300 min      Quality of Isolation 300 \_\_\_\_\_

(Excellent=complete collapse with perfect surgical exposure; Fair=total collapse but the lung has residual air; Poor=no collapse, or partial collapse with interference in surgical exposure)

Incision Time: \_\_\_\_\_      Closure Time: \_\_\_\_\_      Time of OLV \_\_\_\_\_

Sore Throat Post procedure:  
VAS score from page 3

Day 1 \_\_\_\_\_

Day 2 \_\_\_\_\_

Additional Comments/Adverse Events/Other significant intra-operative events

Blocker or Double Lumen Replacement

Replacement Event:	Time	Brief Description of event including duration of replacement event
		Too Deep Too Proximal Other

## Day 1

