## Worst Sore Throat Imaginable

100

## Day 2

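### Hoarseness is a listed outcome, but its only scale is anchored to sore throat and the form has no hoarseness entry, so its incidence cannot be validly compared between devices.

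*Combined protocol and SAP*

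**What the plan says.** - **Objectives.** The additional objective names the two symptoms separately: "post-operatives sore throat, post-operative hoarseness".
- **Outcome Measure(s).** The list includes "incidence of sore throat and/or hoarseness postoperatively", with no case definition for either symptom.
- **Design.** On post-operative days 1 and 2 patients are to be "assessed for hoarseness and sore throat via a VAS scale from 0-100: 0=No sore throat and 100=the worst sore throat imaginable". This is the only instrument given for either symptom.
- **Interventions and Interactions, text.** A study representative is to "evaluate for any postoperative issues such as a sore throat or increase hoarseness on post-operative days 1 and 2". This is described as the patient's last interaction with the study.
- **Interventions and Interactions, schedule table.** The same contact appears as "Patient interviewed on post-op days 1 and 2 to evaluate sore throat", without hoarseness.
- **Appendix 1, data sheet.** The post-operative symptom field is headed "Sore Throat Post procedure", with a Day 1 and a Day 2 score. The scale for each day runs up to "Worst Sore Throat Imaginable". The only other place where a symptom could be written is the line "Additional Comments/Adverse Events/Other significant intra-operative events".
- **Analytical Plan.** Proportions are to be compared by chi-square tests.

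**The concern.** The plan promises an incidence of hoarseness, tells staff to assess it, and then gives them a scale that measures something else and a form with nowhere to put the answer. Hoarseness and sore throat are different symptoms, and the Objectives treat them as such.

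Two problems follow. First, if the scale is applied as the Design section says, a patient with marked hoarseness and no sore throat is recorded as 0. Second, if hoarseness is asked about separately, the answer has no field. It may reach the comments line or it may not, and a blank there could mean absent, not asked or not noted.

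The case definition is also open. One section speaks of an increase in hoarseness, which needs a pre-operative reference that the plan does not collect. Another speaks of incidence.

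At stake is one of the few patient-reported measures of airway morbidity in a trial whose rationale is that the double lumen tube may injure the airway more than a blocker does. Because the day 1 and 2 contact is the last one, a missing answer cannot be collected later.

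**Working it through.** **The plan's own figure.** The only calculated figure is 36 per arm for the repositioning rate (0.5 v 0.3 per hour, SD 0.3, power 80%, type 1 error 5%). Taken as two-sided:

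n = 2 × (0.3/0.2)² × (1.960 + 0.842)² = 2 × 2.25 × 7.85 = 35.3, so 36.

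It reproduces. It concerns repositioning only; no section sizes the trial for hoarseness.

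**Sections side by side.**

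| Place | Sore throat | Hoarseness |
|---|---|---|
| Objectives | named | named |
| Outcome Measure(s) | incidence | incidence |
| Design, days 1 and 2 | 0–100 scale, own anchors | same scale, sore-throat anchors |
| Interventions, text | named | named, as an increase |
| Interventions, schedule table | named | absent |
| Appendix 1, day 1 and 2 scores | entry for each day | none |
| Appendix 1, scale anchors | both anchors | none |

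The lower and upper anchors for both days survive in the text of the form, and the schedule table also names sore throat alone. The gap is therefore unlikely to be an artefact of reading the PDF.

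**Illustration 1: incomplete recording, equal in both arms.** From the documents: 2 × 40 = 80 patients per device, and the chi-square test. Assumed: true incidence 40% v 20%, and the fraction of cases that gets written down. Observed proportion = true proportion × fraction recorded. Power is for the uncorrected two-sided 5% test, by exact binomial enumeration.

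| Fraction recorded | Observed proportions | Power |
|---|---|---|
| 1.00 | 0.40 v 0.20 | 0.801 |
| 0.75 | 0.30 v 0.15 | 0.635 |
| 0.50 | 0.20 v 0.10 | 0.423 |
| 0.25 | 0.10 v 0.05 | 0.209 |

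**Illustration 2: unequal recording with no true difference.** Assumed: 30% hoarse in both arms.

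- Recording 80% v 60%: 0.30 × 0.80 = 0.24 and 0.30 × 0.60 = 0.18, a false gap of 6 points. The test is significant in about 15% of trials.
- Recording 90% v 50%: 0.30 × 0.90 = 0.27 and 0.30 × 0.50 = 0.15, a false gap of 12 points. The test is significant in about 47% of trials.

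The nominal rate is 5%.

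**Illustration 3: the sore-throat scale as a proxy for hoarseness.** Observed proportion = sensitivity × p + (1 − specificity) × (1 − p). With true 40% v 20%, sensitivity 0.8 and specificity 0.9:

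- 0.8 × 0.40 + 0.1 × 0.60 = 0.38
- 0.8 × 0.20 + 0.1 × 0.80 = 0.24

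By the normal approximation, power falls from about 79% to 48%. With sensitivity 0.6 and specificity 0.8 the proportions are 0.36 and 0.28, and power is about 19%.

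**The case against.** The strongest reply is that the protocol twice directs staff to assess hoarseness, so the question is required; only a field and a definition are missing. The Design sentence may simply be loose, with the scale meant for sore throat and hoarseness asked alongside it. No section says that hoarseness will be taken from the comments line, so recording through that line is an inference. The power figures rest wholly on assumed rates, and the assumed 40% v 20% happens to give about 80% power in a trial that was never sized for hoarseness. The documents give no evidence that recording would differ by device. Finally, the outcome list could be read as a composite of the two symptoms, and the documents rank no outcomes, so calling hoarseness secondary is only shorthand.

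Much of this is fair as a limit on size. The figures illustrate and do not measure harm. Unequal recording is a risk and not a finding, although only the surgeon is stated to be blinded and nothing is said of the post-operative interviewer.

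The core point stands. Asking the question does not yield an incidence if the answer has no defined place and a blank has three possible meanings, and no other record is described. The composite reading does not help: scored from this scale, it would still miss the hoarse patient without a sore throat, and the documents do not say which reading applies.

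**Conclusion.** The concern holds. The Objectives, the outcome list, the instrument and the form do not agree on hoarseness, and following the Design section literally gives the wrong score for a patient who is hoarse without a sore throat. As written, the plan cannot deliver a valid comparison of hoarseness incidence between devices.

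The effect is confined to this additional outcome. Its true size cannot be known from the documents, which give no hoarseness rate and no recording rate. Under the assumptions shown, recording half the cases roughly halves power, from 80% to 42%, and recording that differs by arm produces false gaps of 6 to 12 points. The conclusion rests on the text and not on these figures. The correction should be made, and it is cheap.

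**What to change.** 1. Add a hoarseness item to the Day 1 and Day 2 pages of Appendix 1: either yes/no or a separate 0–100 scale running from no hoarseness to the worst hoarseness imaginable. Include a box for not assessed, so that a blank can be interpreted.
2. Correct the Design section so that the existing scale applies to sore throat only, and add hoarseness to the schedule table in Interventions and Interactions.
3. State a case definition for each symptom before analysis, including the cut-off on the sore-throat scale that counts as a case. For hoarseness, say whether a case is any hoarseness or an increase from before surgery; if an increase, add a pre-operative question.
4. Report the two symptoms as separate outcomes. If a composite is also wanted, define it in advance from the two separate items.

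The cost is one extra question in a contact already budgeted at 5–10 minutes, a revised form, and short corrections to the text and table. If the definition is an increase, one pre-operative question is added. No procedure, visit or staff is added.

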At this time, there are a small number of trials looking at the use of the EZ-blocker in adult patients. In one study published in 2013 the EZ-blocker was compared to the Cohen Flex-Tip blocker. In this study they found that time to place the EZ-blocker was in fact shorter and that overall the number of repositioning required was less with the EZ-blocker (6). In 2013, a study was published by Mourisse et al which compared DLT to the EZ-blocker (7). In this study they found initial malposition of both devices to be fairly equivalent, and time to placement was longer with the EZ-blocker. They also found more tracheal and bronchial injuries in the DLT group, but importantly they found that positional stability was equivalent. In both of these studies however they did not design their studies to effectively differentiate between right and left sided procedures when quantifying the need for BB repositioning. Because the take off of the right upper lobe bronchus is sometimes adjacent to, or even proximal to the carina, it can impede effective isolation with a BB. Therefore, claims of positional stability may rely heavily on the laterality of the procedure, with right sided isolation being significantly more labile than left sided especially with respect to isolation using a BB.

In conclusion then, we feel that the potential morbidity of a DLT in terms of the potential for airway injury when compared to a BB suggests that further exploration of the possibility of equivalent positional

stability between these devices is necessary. We feel it is necessary to delineate the impact of laterality on the effectiveness of one technique for isolation versus the other.

In addition to this if there is a difference in stability in cases where right sided isolation via the EZ-blocker fails in the setting of multiple repositions or out and out failure we would like to examine the preoperative CT data to determine if there are anatomic measurement which could potentially inform the appropriateness or inappropriateness of choosing a DLT over an EZ-blocker.

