## **Methods and Measures**

### **Design**

Once the patient is recruited preoperatively in the PAC or within the hospital as an inpatient, this information will be relayed to the study investigators. On the day of surgery, the patient will then be randomized using a random number generator and opaque envelope method for group allocation to either extra-luminal placement of an EZ blocker bronchial blocker or left side double lumen tube. We will recruit at least 80 patients with right sided procedures: 40 EZ-Blocker and 40 left sided DLT. We will also recruit at least 80 patients with left sided procedures: 40 EZ-Blocker and 40 left sided DLT.

We will record age, height, weight, gender, ASA status, type of surgery, side of surgery, duration of one lung ventilation, duration of surgery, and duration of anesthesia.

An IV will be placed in the patient prior to going to the OR. Once in the OR the patient will have routine monitors placed. The patient will be pre-oxygenated with 100% O2 for 2 minutes and induced.. The patient will then be hand ventilated with 100% oxygen for 3 minutes to ensure relaxation. Patients will undergo direct laryngoscopy and according to group assignment will have either an extraluminal EZ-blocker placed or an appropriately sized left sided double lumen placed under the supervision of an attending experienced in thoracic anesthesia and one lung ventilation.

We will confirm endotracheal placement of the ETT or left sided DLT via auscultation and ETCO2. The ETT or DLT will be secured at an appropriated depth. The fiberscope will then be advanced into the lumen of the ETT or DLT to further adjust and confirm placement of the EZ-blocker or DLT. Time for initial bronchial blocker placement or DLT placement will be recorded from the point of the DL to removal of the fiberscope after visualization of the BB with the cuff inflated in the correct position or the DLT with the bronchial cuff inflated.

Other intravascular lines such as a radial arterial line and additional peripheral IV may be placed at the discretion of the attending anesthesiologist.

Once in the final position prior to prepping and draping the blocker or DLT in all groups will be checked to make sure it is still correctly placed with a FOB. The patient will be prepped and draped.

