### **Subjects selection criteria**

Adult patients scheduled for thoracoscopic surgery or thoracotomy requiring lung isolation in which both an EZ-blocker or double lumen tube would be considered an appropriate choice for lung isolation will be recruited.

- Inclusion Criteria**

Patients greater than 18 years of age scheduled for thoracoscopic surgery or thoracotomy requiring lung isolation

Patient presenting as an outpatient for elective thoracic surgery

Inpatients scheduled for thoracic surgery.

- **Exclusion Criteria**

History of difficult airway/intubation  
Patients suspected to have a difficult airway.  
Morbid obesity BMI >39  
Pregnancy  
Emergency status of surgery  
Thoracic surgery requiring a right sided double lumen tube

- **Sample Size**

Assuming a power of 80% and a type 1 error of 5% and a rate of repositioning in the DLT group to be approximately 0.3 repositioning/hour from our experience and a projected rate of repositionings using an EZ-blocker of 0.5 with a standard deviation of 0.3 we estimate a sample size of 36 patients in each arm to demonstrate non-equivalence and so we anticipate enrolling 40 patients in each device in both the left and right sided arm bringing our total enrollment to 160 patients. This is not a multisite study.

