### **Analytical Plan**

Results will be analyzed initially using descriptive statistics. Comparison between groups will be done using chi square tests for proportions, and t-tests or ANOVA procedures for continuous variables. Other inferential statistical analysis will be conducted as appropriate.

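### The CT comparison pools both devices and both sides, so it cannot show for which device or side an anatomic landmark matters

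*Combined protocol and SAP*

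**What the plan says.** Three sections of the combined protocol and SAP bear on the CT work.

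- **Background, Rationale and Context** frames the question, on condition that stability differs, as a look back at scans taken before surgery: "right sided isolation via the EZ-blocker fails in the setting of multiple repositions or out and out failure we would like to examine". This names one device, one side and two kinds of failure.
- **Objectives** is broader. It seeks "anatomic landmarks that may potentially inform the appropriateness or inappropriateness of choosing an EZ-blocker or left sided DLT", with no limit by side or by the device that failed.
- **Design** gives the only working method. Cases: "In patients where isolation is troublesome requiring multiple repositioning we will evaluate their preoperative CT scan". Controls: "We will compare these to an equivalent number of control patients from this study population in which isolation was successful". Matching: "We will attempt to match these patients for size and diagnosis".

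The Design section also lists, among the variables to be recorded, "side of surgery, duration of one lung ventilation, duration of surgery, and duration of anesthesia". The sample size paragraph plans on an hourly scale, with "a rate of repositioning in the DLT group to be approximately 0.3 repositioning/hour from our experience" and 0.5 for the EZ-blocker. The Analytical Plan names no CT analysis; the nearest it comes is "Other inferential statistical analysis will be conducted as appropriate".

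**The concern.** As written, the case group mixes EZ-blocker and double lumen tube (DLT) patients, and right- and left-sided procedures. Controls may come from any of the four groups. Device and side are neither matched nor stratified, so a difference in anatomy between cases and controls could not be assigned to a device or a side. That assignment is what the Objectives need in order to inform the choice of device, and what the Background needs in order to explain right-sided EZ-blocker failure.

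Two smaller gaps follow from the same rule. A device that fails outright after few repositionings is not a case, and it is hardly a success that could serve as a control. Case status also depends on how long the lung was isolated, and the comparison makes no allowance for this although OLV duration is recorded.

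At stake is the usefulness of an additional objective that has no power statement of its own.

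**Working it through.** **The plan's own figure.** The CT comparison has none. The sample size paragraph supplies the rates, and its figure reproduces: 2 × (1.96 + 0.842)² × 0.3² / 0.2² = 35.3, so 36 per arm (two-sided 5%, 80% power).

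**Inputs from the documents.** 40 patients in each of four device-and-side groups; 0.5 per hour for EZ-blocker and 0.3 per hour for DLT.

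**Assumptions, not in the documents.** Poisson counts; the same rate on both sides; 2 h of OLV for everyone; a case is 2 or more repositionings and every other patient is a success; a landmark present in 25% of patients doubles the rate only in right-sided EZ-blocker patients.

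**Case probabilities.** P(X ≥ 2) = 1 − e^(−m)(1 + m), with m = rate × hours. In right-sided EZ-blocker patients the rate without the landmark is 0.5 / (0.75 + 0.25 × 2) = 0.4 per hour, and with it 0.8 per hour. At 2 h the probabilities are 0.191 and 0.475, a risk ratio of 2.48. They are 0.264 for left EZ-blocker and 0.122 for each DLT group.

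**Expected cases.**

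| Group | Landmark (10 patients) | No landmark (30 patients) |
|---|---|---|
| Right EZ-blocker | 4.75 | 5.74 |
| Left EZ-blocker | 2.64 | 7.93 |
| Right DLT | 1.22 | 3.66 |
| Left DLT | 1.22 | 3.66 |
| All | 9.83 of 40 | 20.98 of 120 |

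**Odds ratios.**

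- Right EZ-blocker cases, same-group controls: (4.75 × 24.26) / (5.74 × 5.25) = 3.83.
- Pooled cases and controls: (9.83 × 99.02) / (20.98 × 30.17) = 1.54. Right EZ-blocker patients are 10.49 of 30.81 cases, or 34%.
- Right EZ-blocker cases, controls from any group: (4.75 / 5.74) / (30.17 / 99.02) = 2.72. This does not understate the risk ratio of 2.48.

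**Where the landmark acts.** The pooled odds ratio is 1.54 if it acts in right EZ-blocker only, 1.94 on the right side with both devices, 2.29 in both EZ-blocker groups, and 3.56 in all four groups.

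**Sensitivity.** Inputs were varied over OLV 1 to 4 h, prevalence 10 to 50%, rate ratio 1.5 to 3, and left EZ-blocker at 0.3 or 0.5 per hour. With the landmark acting only in right EZ-blocker patients, the pooled log odds ratio keeps 33 to 72% of the log risk ratio. With left EZ-blocker at 0.3 per hour in the main setting, the pooled odds ratio is 1.65.

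**Exposure time.** At 0.5 per hour the chance of becoming a case is 9% at 1 h, 26% at 2 h, 44% at 3 h and 59% at 4 h.

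**Check against the plan's SD.** A Poisson count at 0.5 per hour over t hours gives an hourly-rate SD of √(0.5 / t), which is 0.50 at 2 h. The plan assumes 0.3, which would need 0.5 / 0.09 = 5.6 h. The illustration is therefore noisier than the plan's own assumption.

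**The case against.** The strongest reply is that the Objectives, not the Background, set the aim, and they limit neither side nor failing device. The wide scope in the Design section fits them, and if a landmark acts in all four groups pooling costs almost nothing. This stands in part. It rules out treating right-sided EZ-blocker failure as the only legitimate target. It does not rescue the pooled comparison, because choosing between devices still requires knowing for which device a landmark matters.

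A second reply is that the Design text should be read through the Background, with right-sided EZ-blocker cases only. The dilution then disappears, and any-group controls do not understate the risk ratio. The missing route for outright failure and the lack of allowance for OLV time remain.

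Stronger readings that a reader might infer are not supported:

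- *Pooling is why a landmark would be missed.* In simulation (OLV mean 2 h, coefficient of variation 0.4), detection at 5% is 9% pooled and still only 20% with right EZ-blocker cases and same-group 1:1 controls. The rise to 37% comes from using all same-group successes, and to 53% from a per-hour count model on all 40 patients. Most of that gain is a design extension, not a repair of the mismatch. With overdispersed counts the four figures are 6%, 10%, 21% and 35%.
- *OLV time biases the result.* Nothing in the documents links OLV time to anatomy. It is shown only to add noise.
- *Device confounds the anatomy comparison.* Device is randomised, so it is unrelated to anatomy except by chance.
- *One third of cases come from the target group.* The 34% assumes equal rates on both sides, whereas the Background expects the right side to be less stable. With left EZ-blocker at 0.3 per hour it is 42%.

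**Conclusion.** The point holds as a minor one. The CT method selects cases by repeated repositioning across both devices and sides and draws unstratified controls, so it cannot show where a landmark matters. It would dilute a landmark confined to one group: an odds ratio of 3.8 becomes 1.5 in the illustration. There is almost no loss if the landmark acts in all four groups, and no such dilution if only right-sided EZ-blocker cases were intended.

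The textual finding needs no model. The figures rest on assumed prevalence, effect, OLV time and Poisson counts, and on a larger spread than the plan's own SD. They, and the detection rates, show direction only. The number of outright failures that the case rule would leave out cannot be estimated from the documents. The documents do not support reading this as a threat to the primary device comparison, which is unaffected.

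**What to change.** Reconcile the Background, Objectives and Design text on the CT question, including whether it still depends on a difference in stability. Then state in the Design section:

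1. The comparison is run within device-and-side group. Right-sided EZ-blocker is reported first, and the other three groups are reported separately, which respects the breadth of the Objectives.
2. Controls come from the same device-and-side group, with the repositioning count that makes a case and the meaning of successful isolation written down.
3. Outright failure counts as a case. The data form has no dedicated field for it, so it must come from the free-text event record or from an added tick box.
4. OLV hours are accounted for, to reduce noise.
5. Where scans are available, all same-group successes are used instead of forcing 1:1. Reading all 40 right-sided EZ-blocker scans and modelling repositionings per hour is an optional extension.

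**Cost.** Side, OLV duration and replacement counts are already recorded. Stratifying with 1:1 controls adds no CT reads while same-group controls suffice. At 2 h, under the assumptions above and with no landmark effect, the plan as written needs about 2 × 30.9 = 62 reads. Reading all 40 right-sided EZ-blocker scans and keeping 1:1 in the other groups needs 40 + 2 × 20.3 = 81, about 19 more (about 33 more at 1 h, 5 more at 3 h). Using all successes in every group would approach all 160 scans.

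Estimates stay imprecise even so. For a true rate ratio of 2, 80% of simulated estimates from the count model fall between 1.3 and 3.1, or between 0.9 and 3.8 if counts are overdispersed.
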